Study Title:

Efficacy of Multimodal Periarticular Injections in Operatively Treated Ankle Fractures: A Randomized Controlled Trial

Date: 8/8/2016

NCT: NCT02967172

Statistical Analysis Plan:

We will compare the two groups by improvement in the following measures:

Visual Analog Scores scores recorded as Standard of Care during daily rounds
Patient controlled analgesia usage as recorded as Standard of Care in Medical Record
Time spent in hospital
Standard of care outcome measures noted in Patient Medical Record

Standard statistical analysis will be performed to analyze differences between groups. ANOVA, T-Test, and Kolmogorov-Smirnov, and other tests will be used.

Based on a power analysis we estimate a minimal sample size of forty patients in each group to detect a 1.5 point difference in the Visual Analog Score (VAS) at each recording, with a standard deviation of 2.0 points, a p-value of .05, and a power of 80% or higher. Additional subjects (total subjects = 200) will aid in subgroup analyses, and ensure that we maintain an adequate sample size even if we run into issues with patient compliance (e.g. refusal of VAS during post-op stay) or unintentional de-blinding (nurse, student, resident etc. accidentally telling patient their treatment assignment) following the procedure.

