All patients included in the study will receive standard post-operative opioid analgesic regimens, administered ‘per needed’, regardless of their assigned treatment group per study protocol. ≥ 40 patients will be randomly assigned to each group. The patients enrolled in the investigation as well as health care professionals performing post-operative assessments and collecting data will be blinded to treatment allocation.

The feasibility of multimodal peri-incisional injections is supported by their current efficacy in populations undergoing elective orthopedic surgeries. These injections may be equally effective at reducing pain compared to regional anesthesia with continuous infusions, and single-shot nerve blocks.[7, 8]

We hypothesize that the injection cohort will have reduced pain scores, lower narcotic requirements, shorter length of stay, and be more likely to discharge to home following surgery.

We aim to evaluate the effectiveness of peri-incisional multimodal injections as an alternative post-operative pain control method in orthopaedic trauma patients with operative, closed, rotational ankle fractures. Patients undergoing surgical internal fixation of such fractures will be randomized to either receive or not receive intra-operative injections in addition to standard opioid analgesic regimens.

Control group will receive no injection and will receive IV and oral analgesics post-operatively.

Treatment group will receive injection during surgery into the periarticular space of ropivacaine, morphine, and epinephrine. They will also be provided with IV and oral analgesics post-operatively.

We will evaluate effectiveness of intra-operative injections by assessing inter-group differences in post-operative pain management outcomes, including: (1) subjective patient pain levels via visual analog scales in the immediate postoperative period; (2) quantity of opioid analgesics required prior to discharge; (3) post-operative length of stay; (4) discharge status (e.g. SNF, Rehab, Home).

We hypothesize that the injection cohort will have reduced pain scores, lower narcotic requirements, shorter length of stay, and be more likely to discharge to home following surgery.

Following consent, patients will be randomized by the research team using Microsoft Word (R) Random Number Generator.

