Patients will be blinded as to whether they received the injection or not. This is possible as they will be unconscious in surgery during their procedure. While an inpatient, the patients will be notified that they may ask which arm of the study they are in during their 3 month followup visit***. Until then they will stay blinded.

They will then be treated with internal fixation of their fracture(s) as per standard of care.

During this surgery, patients randomized to the peri-incisional injection cohort will receive a single, 25 mL intra-operative injection with medication following completion of fracture fixation and just prior to skin closure. The injection will be administered as such:

20 mL injected into the peri-incisional soft tissues in a circumferential fashion.

5mL injected into the ankle joint.

This will take approximately 2 minutes of total surgery time.

Following surgery, patients in the treatment and non-treatment groups will both be provided with the same intravenous (patient-controlled analgesia) and oral pain medications scheduled "per needed".

Following surgery, (and again at their followup visits up to 3 months following surgery) the research team will examine the patient medical record and record narcotic use by the patient during their hospital stay. They will also record clinical outcomes from the medical record. (Notably VAS score). At 3 months the patient will no longer be followed in the study. At this point, the patients requesting information on which treatment arm they were in can be told.

No follow-up after 3 months.

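### The protocol's first-listed outcome is pain in the immediate postoperative period, but the SAP's only named VAS source is daily rounds, which is not anchored to the end of surgery and may miss or dilute an early effect.

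*SAP*

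**What the plan says.** The protocol's list of outcomes begins with "subjective patient pain levels via visual analog scales in the immediate postoperative period". No outcome is called primary, so this one is first in listing order only. It is, however, the only outcome with a sample-size calculation.

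The SAP's list of measures has one VAS entry: "Visual Analog Scores scores recorded as Standard of Care during daily rounds". Its power paragraph sizes the trial to "detect a 1.5 point difference in the Visual Analog Score (VAS) at each recording".

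On the source of the data, the protocol's account of procedures says: "They will also record clinical outcomes from the medical record. (Notably VAS score". It names no time point and does not limit the scores to rounds. The same account describes the treatment as a "single, 25 mL intra-operative injection with medication following completion of fracture fixation and just prior to skin closure". There is no repeat injection, and both arms then receive the same intravenous and oral analgesia as needed.

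Neither document gives a time of rounds, a number of rounds per day, hours since surgery for any score, a recovery-room score, a definition of immediate, or a rule for choosing the score to analyse.

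**The concern.** The two descriptions of VAS use different clocks. The protocol's outcome is tied to the end of the operation. The SAP's measurement is tied to when the ward team comes round. Because the injection is given once, at the end of surgery, the delay from injection to first score depends on when the operation finished. Patients at different hours after injection are then pooled as one recording.

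If the injection's effect is short compared with that delay, some or all first scores are taken after it has ended. The observed difference shrinks towards zero, and mixing patients with and without a current effect adds variance in the injection arm. A null VAS result could then reflect when pain was scored and not whether the injection relieved pain in the period the protocol asks about.

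**Working it through.** **Step 1: the plan's own sample size.** Inputs from the SAP are a difference of 1.5, SD 2.0, significance level .05 (taken as two-sided, since the SAP does not say), power of 80% or higher, and 40 per group.

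- Normal approximation: n per group = 2 × (z₀.₉₇₅ + z_power)² × SD² / difference².
- At 80% power: 2 × (1.960 + 0.842)² × 4 / 2.25 = 27.9, so 28 (29 by noncentral t).
- At 90% power: 2 × (1.960 + 1.282)² × 4 / 2.25 = 37.4, so 38 (39 by noncentral t).
- Power with 40 per group: 91.8% (91.2% by noncentral t).

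Forty per group therefore satisfies the SAP's power statement with some margin. The number is not in dispute, but it requires the full 1.5 points to be present at the recording analysed.

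**Step 2: dilution without assuming any clock times.** Let f be the share of first scores taken while the effect is present, with 1.5 points in that share and zero in the rest. The mean difference is 1.5 × f. With SD 2.0, two-sided .05 and the normal approximation:

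| f | Mean difference | Power, 40 per group | Power, 100 per group | n per group for 80% |
|---|---|---|---|---|
| 1.00 | 1.50 | 91.8% | >99.9% | 28 |
| 0.75 | 1.125 | 71.1% | 97.8% | 50 |
| 0.50 | 0.75 | 38.9% | 75.5% | 112 |
| 0.25 | 0.375 | 13.1% | 26.3% | 447 |

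The documents do not give f. The 100 per group assumes that the planned 200 are split 1:1.

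**Step 3: one set of clock times.** These are assumptions and are not in the documents: rounds at 07:00, surgery ending uniformly between 09:00 and 18:00, and an effect of 1.5 points that lasts D hours and then stops.

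- Surgery ending at 18:00 gives a first score at 13 h, and surgery ending at 09:00 gives one at 22 h. The range is 9 h wide.
- Share scored while the effect is active: f = (D − 13) / 9, limited to between 0 and 1.
- Variance in the injection arm: 4 + f(1 − f) × 1.5². In the control arm: 4. The pooled SD is the square root of their average.
- Example, D = 16: f = 3/9 = 0.333; difference = 0.50; injection-arm variance = 4 + 0.222 × 2.25 = 4.50; pooled SD = √4.25 = 2.06.

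Power by noncentral t, two-sided .05:

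| Effect lasts | f | Mean difference | 40 per group | 100 per group |
|---|---|---|---|---|
| 12 h | 0 | 0 | no effect to detect | no effect to detect |
| 16 h | 33% | 0.50 | 19% | 40% |
| 18 h | 56% | 0.83 | 43% | 81% |
| 20 h | 78% | 1.17 | 71% | 98% |
| 22 h or more | 100% | 1.50 | 91% | >99% |

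The result runs from complete loss to no loss, depending on a duration that the documents do not give.

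**The case against.** Several objections have force.

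- **The wording may not conflict.** The protocol follows patients for 3 months. Against that horizon, the immediate postoperative period could mean the inpatient stay, which rounds scores do cover. On that reading the fault is an undefined time point, not a contradiction. This stands as a possible reading, but the first score would still come at an uncontrolled interval after the injection.
- **Rounds may not be once a day.** The SAP gives neither their number nor their time, and it refers to more than one recording. A round on the evening of surgery is not excluded. This stands, and it is why Step 3 is only an illustration.
- **No time course is stated.** The documents fix when the injection is given, not how long it acts. A missed window is therefore a possibility and has not been demonstrated.
- **The full sample protects against moderate dilution.** With 100 per group, power still reaches 80% in the 18 h and 20 h cases. It does not in the 16 h case, nor in Step 2 when half the scores are late.
- **Early benefit may show elsewhere.** Patient-controlled analgesia use and opioid quantity can reflect early need. The SAP's general item on routine chart outcomes, or the protocol's chart-based VAS, could also admit earlier scores. Neither names one, and the specific VAS entry points to rounds.

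A reader might infer that the trial will miss the injection's effect, or that the comparison is biased. The documents support neither. Too little is stated to say how much is lost, and randomisation balances the surgery-to-rounds interval between arms on average.

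**Conclusion.** The point holds in a conditional form. The SAP's stated VAS source is not anchored to the end of surgery, while the protocol's outcome and its one-time treatment both are. Following the SAP as written can leave the early hours unscored, and it pools different hours since injection. The harm is dilution and added variance.

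The size is open. Under the assumptions of Step 3, power with 40 per group lies between 19% and 91% for effects lasting 16 to 22 h, with nothing to detect at 12 h. These figures concern the first score only and rest on an assumed time of rounds, an assumed spread of operating times and an on/off effect. They show what is at stake and do not forecast the result.

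It would also be wrong to infer that the sample size is in error: 40 per group meets its stated target. This is an inexpensive improvement that should be made, since it determines whether the first-listed outcome is measured in the period it names.

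**What to change.** **SAP, first measure.** Replace the rounds-based source with VAS scores in the medical record (recovery room and ward, as routinely charted), indexed by hours from end of surgery over the first 24 h. Use the score nearest each chosen time within a stated window.

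**Main comparison.** Name one early time point, or a time-weighted 0 to 24 h average, as the main VAS comparison. Treat the other times and the daily-rounds scores as supportive. This also settles which recording the 1.5-point calculation refers to.

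**Data extraction.** Record the timestamp of each score and of the end of surgery.

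**If the chart holds only rounds scores.** Record hours since end of surgery for each score and include a treatment-by-time term. A covariate for time alone would still estimate roughly the average, diluted difference. Restate the protocol's first outcome as pain at daily rounds.

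**Cost.** Charting times are irregular, so windows are needed and some scores will fall outside them. Chart extraction takes slightly more work. No extra visit or assessment is needed if recovery-room and ward scores are routinely charted, which is an assumption to confirm. The 40 per group does not change.

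### The only opioid measure the SAP names is PCA usage, but the protocol's outcome is opioid quantity before discharge, without limit by route

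*SAP*

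**What the plan says.** **Outcome and hypothesis (Protocol).** The second item in the list of post-operative outcomes is "2) quantity of opioid analgesics required prior to discharge", with no restriction by route. The matching hypothesis reads "We hypothesize that the injection cohort will have reduced pain scores, lower narcotic requirements".

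**Treatment (Protocol).** The regimen is described as an opioid one in both arms: "All patients included in the study will receive standard post-operative opioid analgesic regimens". For controls, "Control group will receive no injection and will receive IV and oral analgesics post-operatively"; for the injection arm, "They will also be provided with IV and oral analgesics post-operatively". The description of post-operative care adds that "patients in the treatment and non-treatment groups will both be provided with the same intravenous (patient-controlled analgesia) and oral pain medications", to be taken as needed.

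**Data collection (Protocol).** The team will review the medical record and "record narcotic use by the patient during their hospital stay", again without limit by route.

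**Analysis (SAP, list of measures).** The groups are to be compared on four items: VAS, "Patient controlled analgesia usage as recorded as Standard of Care in Medical Record", time in hospital, and a general item for routine-care outcomes found in the record. The second is the only one that names an opioid measure. The list is not stated to be exhaustive. The SAP does not mention oral opioid use, a total across routes, or a way of combining drugs.

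**The concern.** The analysis plan names a part of the protocol's outcome and never names the outcome itself. If the opioid hypothesis is tested on PCA usage, oral opioid taken on the ward does not count. A patient who moves from PCA to oral medication then appears to need less opioid although the total has not changed. The reverse shift can hide a real saving.

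Providing the same drugs to both arms does not prevent this. They are taken as needed, so actual use can differ. The PCA/oral split also arises after randomization and may itself respond to the injection, so randomization does not make it equal.

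Reducing opioid reliance is one of the trial's stated goals, and this is one of its four hypotheses. A reader of the results would take a difference in PCA usage as evidence on that goal.

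**Working it through.** **Plan's own figure.** There is none to reproduce for opioid use: no effect size, standard deviation or power is given. The SAP's only power calculation is for VAS (1.5-point difference, SD 2.0, 40 per group), and it does not depend on which opioid measure is used.

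**Inputs.** From the documents: both arms receive PCA and oral medication as needed; the outcome is not limited by route; the SAP names PCA only. Not in the documents, so assumed: that some oral drugs are opioids, the oral share of opioid use, and any difference in that share between arms.

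**Formula.** Let T be mean total opioid use in an arm and s the oral share of that total, with subscript 0 for control and 1 for injection. PCA use is (1 − s)T, so

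PCA ratio = (T1/T0) × (1 − s1)/(1 − s0).

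This is an identity. PCA usage and total use show the same relative saving only when s1 = s0.

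**False saving.** Set T1 = T0 (no true saving) and s1 = s0 + 0.05:

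| s0 | PCA ratio | Apparent saving |
|---|---|---|
| 0.25 | 0.70/0.75 = 0.933 | 6.7% |
| 0.50 | 0.45/0.50 = 0.90 | 10% |
| 0.75 | 0.20/0.25 = 0.80 | 20% |

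**Hidden saving.** Set s1 = s0 − 0.05 and find the true total saving at which the PCA ratio equals 1, namely 1 − (1 − s0)/(1 − s1):

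| s0 | (1 − s1)/(1 − s0) | True saving that reads as zero |
|---|---|---|
| 0.25 | 0.80/0.75 = 1.067 | 6.3% |
| 0.50 | 0.55/0.50 = 1.10 | 9.1% |
| 0.75 | 0.30/0.25 = 1.20 | 16.7% |

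**Dependence on the assumed shift.** With equal totals and an oral share higher by d, the apparent saving is d/(1 − s0), which is proportional to d. Doubling the shift to 10 points doubles the first set of figures to 13.3%, 20% and 40%. A shift of zero gives no error.

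**Does the SAP's fourth item restore the total?** It names no drug, route, total or conversion. The protocol's data-collection paragraph also lists narcotic use separately from clinical outcomes. An analyst could report PCA alone, or a total of their own choosing, and comply with the SAP either way.

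**The case against.** The strongest reply is that the SAP list is not a one-to-one restatement of the protocol's outcomes. Discharge status is a protocol outcome too, and it is not named in the SAP either; unless it was dropped, it must fall under the general fourth item. If that item can carry one unnamed outcome it can carry another, and narcotic use comes from the same record. The protocol already defines the outcome and plans the data collection, so only a line of SAP text is missing. That reading is possible but not compelled, and a plan that permits both readings does not fix the measure before the data are seen.

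Second, no passage says that an oral drug is an opioid, and PCA alone could satisfy the description of an opioid regimen. This stands as a limit. Oral opioid use is a reasonable inference, and if it is wrong PCA usage loses nothing to the oral route.

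Third, the shares and the 5-point shift have no source in the documents, which offer no evidence that the split differs between arms; patients and post-operative assessors are also blinded. This stands against any claim about the actual size. It does not show that the splits will be equal, since blinded patients whose pain differs may still use the two routes differently.

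Finally, morphine equivalents and a start at the end of surgery are not in the documents, and such a start leaves out the morphine in the injection itself. A post-operative start fits the protocol's description of these as post-operative outcomes, but the exclusion is a choice the SAP should state.

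**Conclusion.** The concern holds and should be fixed. The protocol's opioid outcome and the SAP's named opioid measure are different quantities, and they agree in relative terms only if the oral share of opioid use is equal in the two arms.

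The actual error cannot be determined from the documents. Under the assumed shares and a 5-point difference, PCA usage could show a saving of 6.7% to 20% when there is none, or read as zero when the true saving is 6.3% to 16.7%. The error is zero if the split is equal or if no oral drug is an opioid.

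Confidence is high on the mismatch between the texts; its numerical consequence is illustrative. The effect is confined to one of four hypotheses, which has no power calculation. The VAS comparison is untouched.

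**What to change.** Replace the PCA item in the SAP list with total post-operative in-hospital opioid use by all routes, in morphine equivalents, from end of surgery to discharge. Keep PCA usage as a descriptive component. The same entry should name the conversion method and state that morphine given in the intra-operative injection is outside the measure. If no oral drug in the regimen is an opioid, the SAP should say so.

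The cost is a short change to the SAP, plus abstraction and conversion of oral opioid doses from records the team already plans to review for narcotic use. No extra patients or visits are needed, and treatment does not change.

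### No covariate-adjusted analysis is prespecified; naming baseline covariates in advance would narrow the confidence intervals, provided the chart holds those variables

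*SAP*

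**What the plan says.** The SAP lists what will be compared between arms: improvement in VAS from daily rounds, patient-controlled analgesia use, time in hospital, and other outcomes in the record. On method it says "Standard statistical analysis will be performed to analyze differences between groups" and names ANOVA, the t-test and Kolmogorov-Smirnov, plus other tests that it does not identify. It names no covariate and no regression model.

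On allocation the protocol says "Following consent, patients will be randomized by the research team using Microsoft Word (R) Random Number Generator". No stratification factor or block size is given.

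On data, the protocol says that after surgery and at follow-up visits "the research team will examine the patient medical record and record narcotic use by the patient during their hospital stay", together with clinical outcomes, VAS in particular. No pre-operative or other baseline variable appears among the items to be recorded.

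The sample-size paragraph in the SAP says "we estimate a minimal sample size of forty patients in each group" is needed "to detect a 1.5 point difference in the Visual Analog Score (VAS) at each recording", "with a standard deviation of 2.0 points", a significance level of .05 and "a power of 80% or higher". It adds: "Additional subjects (total subjects = 200) will aid in subgroup analyses".

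**The concern.** With two arms and no covariate named, the three listed tests read as unadjusted comparisons. If part of the patient-to-patient variation in pain or opioid use can be predicted from information available before surgery, that part stays in the error term. The intervals are then wider than they need be. A linear model with treatment and prespecified baseline covariates estimates the same mean difference under randomisation, with a smaller residual variance to the extent that the covariates predict outcome.

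Two features of the plan make prespecification worthwhile. First, the open reference to further tests would let an adjusted model be chosen after the results are seen, so a reader could not tell a planned adjustment from a selected one. Second, the SAP speaks of improvement in VAS without defining a reference time. If that came to mean a simple change from a pre-operative score, the comparison could be less precise than one of the raw post-operative scores, whereas adjustment for the pre-operative score avoids that loss.

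**Working it through.** **Inputs from the SAP's sample-size paragraph:** difference 1.5 points, SD 2.0, significance level .05, power at least 80%, minimum 40 per group, 200 in total.

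**Assumptions:** two-sided testing; 1:1 allocation, so 100 per group; SD 2.0 is the SD of the raw VAS score (the SAP does not say); combined correlation r of the covariates with VAS from 0.3 to 0.6, with 0.2 shown as a pessimistic case. No document gives r.

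**Step 1: the plan's own figure.** n per group = 2(1.960 + 0.842)² × 2.0² / 1.5² = 27.9, so 28 (29 with the t distribution). The stated 40 is not the minimum for 80% power. It is close to the 90% figure (38, or 39 with t) and satisfies the plan's wording of 80% or more. The number is conservative.

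**Step 2: power without adjustment.** SE = 2.0 × √(2/n).
- 40 per group: SE = 0.447; 1.5/0.447 = 3.354; power = Φ(3.354 − 1.960) = 91.8% (91.2% with t).
- 100 per group: SE = 0.283; 1.5/0.283 = 5.303; power = Φ(5.303 − 1.960) = 99.96% (99.95% with t).

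**Step 3: adjustment.** Residual SD = 2.0 × √(1 − r²); 95% CI half-width = 1.96 × residual SD × √(2/n); narrowing = 1 − √(1 − r²). Power is by the normal approximation.

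| Assumed r | Residual SD | Half-width, 40 per group | Half-width, 100 per group | CI narrowing | Power for 1.5, 40 per group |
|---|---|---|---|---|---|
| 0 | 2.000 | 0.88 | 0.55 | 0 | 91.8% |
| 0.2 | 1.960 | 0.86 | 0.54 | 2.0% | 92.8% |
| 0.3 | 1.908 | 0.84 | 0.53 | 4.6% | 94.0% |
| 0.5 | 1.732 | 0.76 | 0.48 | 13.4% | 97.2% |
| 0.6 | 1.600 | 0.70 | 0.44 | 20.0% | 98.7% |

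At 100 per group, power exceeds 99.9% in every row.

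**Step 4: a smaller subgroup.** The SAP names no subgroup or size; 25 per arm is purely illustrative. Unadjusted: SE = 2.0 × √(2/25) = 0.566, 1.5/0.566 = 2.652, power 75.5% (74% with t). At r = 0.5: SE = 0.490, 1.5/0.490 = 3.062, power 86.5% (85% with t).

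**Step 5: if improvement means change from a pre-operative score.** Take r as the correlation of pre-operative with post-operative VAS, and the same SD of 2.0 at both times. The change-score SD is 2.0 × √(2(1 − r)). At r = 0.3 this is 2.366, and power at 40 per group is 80.9%. Adjusting for the same score gives 94.0%. The change score has a larger variance than the raw score whenever r is below 0.5; the adjusted analysis has a variance no larger than either.

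No corresponding figures can be given for opioid use or time in hospital, because the SAP states no SD or effect for them.

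**The case against.** The strongest reply is that the planned comparison does not need this. On the plan's own inputs, the unadjusted t-test has about 91% power at the minimum size and over 99.9% at the planned size. That stands: nothing here puts the 1.5-point VAS comparison at risk.

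A reader might infer four stronger things, none of which the documents support.

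- *Strong predictors are already in the extracted data.* The listed items are in-hospital narcotic use and clinical outcomes. Whether usable baseline variables are in the chart, and how strongly they predict outcome, is unknown.
- *The plan throws precision away.* The SAP leaves further tests open and does not limit ANOVA to a one-way model. Adjustment is unspecified, not excluded.
- *The unadjusted comparison is biased by chance imbalance.* Randomisation makes it unbiased, and its type I error already allows for such imbalance.
- *The allocation list should be redrawn with strata.* The protocol is silent on strata and blocks, but that silence does not show a defect that needs a new list. The precision can be gained in the analysis.

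Two further limits are fair. Entry is restricted to closed, rotational, operatively treated fractures, which may reduce how much fracture pattern predicts. And at r = 0.2 the gain is only 2%.

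**Conclusion.** The point holds as a gap in prespecification with a modest cost in precision. No covariate is named for any comparison, and no stratification is described that would call for one. Under an assumed r of 0.3 to 0.6, prespecified adjustment narrows the VAS confidence interval by about 5% to 20%; at r = 0.5 this is a half-width of 0.48 instead of 0.55 points at 100 per group. The benefit would matter most in the subgroup analyses, where numbers are smaller. It is neither a correction of bias nor a rescue of an underpowered trial. The size rests on the assumed r, on SD 2.0 being a raw-score SD, and on the baseline variables being present in the chart.

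**What to change.** Before unblinding, confirm which baseline variables the medical record holds, and amend the SAP as follows.

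- Analyse VAS by a linear model with treatment, adjusted for the last pre-operative VAS in the record (with a missing-indicator where there is none), age, fracture pattern and pre-injury opioid use. Omit any variable that proves not to be recorded, and settle this before outcomes are compared by arm.
- Report the adjusted mean difference with its 95% CI, and keep the unadjusted t-test as a sensitivity analysis.
- Use the same covariates for opioid use, on a scale suited to skewed data, chosen in advance.
- State which VAS recording or recordings the model applies to, since the SAP refers to each recording.

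The cost is a paragraph of SAP text and up to four baseline fields from a record the team already reads. The downsides are slightly more chart extraction and some missing pre-operative VAS scores. Treatment, allocation and sample size are unchanged.

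### VAS pain is powered separately at every recording at an unadjusted .05, and neither document says which recording, summary or test decides efficacy

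*SAP*

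**What the plan says.** The SAP's list of measures opens with "We will compare the two groups by improvement in the following measures". Four items follow without ranking. The first is "Visual Analog Scores scores recorded as Standard of Care during daily rounds". The opioid item comes second and reads "Patient controlled analgesia usage as recorded as Standard of Care in Medical Record". The third is length of hospital stay, and the last is the open-ended "Standard of care outcome measures noted in Patient Medical Record". On methods it says that "ANOVA, T-Test, and Kolmogorov-Smirnov, and other tests will be used", and it matches no test to any measure.

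The sample-size paragraph gives at least 40 patients per group to "detect a 1.5 point difference in the Visual Analog Score (VAS) at each recording", with SD 2.0, p = .05 and power of 80% or more. It adds that "Additional subjects (total subjects = 200) will aid in subgroup analyses"; the subgroups are not named.

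The Protocol's numbered outcomes begin with "subjective patient pain levels via visual analog scales in the immediate postoperative period", followed by opioid quantity before discharge, length of stay and discharge status. Its hypothesis covers all four together. Its closing description of data collection has the team review the record after surgery and again at follow-up visits to 3 months, and singles out VAS among the clinical outcomes to be taken from it.

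Neither document labels an outcome primary or states a multiplicity rule.

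**The concern.** VAS is recorded repeatedly, and the plan applies the .05 level to each recording. It does not say whether one significant recording is enough, whether all must be significant, or whether the recordings are to be combined. Nor does it fix which recordings count. The SAP's daily rounds and the Protocol's postoperative wording point to inpatient scores, but the record review up to 3 months leaves the set open. The number of inpatient recordings also depends on length of stay, which is itself an outcome.

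The stake is that the decision rule could be settled after the data are seen. One choice pushes the false-positive rate above the stated 5%; the other pushes power below the per-recording figure. A reader of the results could not tell a planned finding from a selected one.

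A separate definitional gap concerns opioids. The SAP counts patient-controlled analgesia only, while the Protocol also gives oral analgesics and speaks of opioids or narcotics generally up to discharge.

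**Working it through.** **Inputs from the SAP:** difference 1.5, SD 2.0 (standardised effect 1.5/2.0 = 0.75), p = .05, power at least 80%, minimum 40 per group, total 200.

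**Assumed, because not stated:** two-sided testing; 1:1 allocation (so 100 per group); two, three or five VAS recordings; equal correlation of 0.5 to 0.9 between recordings; complete data.

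**1. The plan's own figure, one recording.** n per group = 2(1.96 + 0.842)²/0.75² = 27.9, so 28, or 29 with the t-test. At 90% power it is 38, or 39 with the t-test. With 40 per group the non-centrality is 0.75 × √(40/2) = 3.35 and t-test power is 91.2%. With 100 per group it is 99.95%. So 40 meets the SAP's condition of 80% or higher for a single recording.

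**2. Two rules the text allows.** Simulated two-sided t-tests at .05, 200,000 runs per cell. Ranges run from the lowest to the highest value over correlations 0.5 to 0.9.

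| Recordings | No effect: any one significant | Constant 1.5 points, 40 per group: all significant |
|---|---|---|
| 2 | 7.0–9.1% | 85.0–88.3% |
| 3 | 8.4–12.6% | 80.3–86.6% |
| 5 | 10.2–18.2% | 73.5–84.5% |

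The false-positive column was run at 100 per group; at 40 per group the values differ by less than 0.2 points. As a ceiling, independent recordings would give 1 − 0.95^k: 9.8%, 14.3% and 22.6% for k = 2, 3 and 5.

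These are two-sided rates. By symmetry about half would favour the injection: 7.0/2 = 3.5% to 18.2/2 = 9.1%, against a nominal 2.5%.

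Requiring all recordings causes no inflation (0.3 to 2.3% for three recordings). At 100 per group its power for a constant 1.5 points is at least 99.79% in every case.

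**3. One averaged effect instead.** The mean of two recordings with correlation r has SD 2.0 × √((1 + r)/2), which is 1.73 at r = 0.5 and 1.95 at r = 0.9. For a constant 1.5 points, power at 40 per group is 96.9% and 92.5%. If the effect fades from 1.5 to 0.75 (assumed), the mean effect is (1.5 + 0.75)/2 = 1.125. Power is then 72.2 to 81.8% at 40 per group and 98.2 to 99.5% at 100.

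**The case against.** The strongest reply is that the main outcome is clear in practice. VAS comes first in both documents and is the only outcome with a power calculation, and the Protocol narrows it to the early postoperative period. At 200 patients a constant 1.5-point effect would be found under either rule. The first part stands as far as it goes: VAS is the implied main outcome. But that does not choose among its recordings, and more patients do not repair a false-positive rate.

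Several stronger readings are tempting, and the documents do not support them:

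- *The trial is too small.* It is not. For one recording, 40 per group exceeds the 29 needed for 80% power.
- *Any of the four measures can prove efficacy.* No text says so, and the Protocol's hypothesis joins its outcomes with *and*. The false-positive range above therefore counts VAS recordings only.
- *Improvement implies a missing baseline VAS.* The SAP applies the word to time in hospital too, which has no baseline. It more naturally means better results in one group.
- *Opioid use is defined in three conflicting ways.* The Protocol's two descriptions are nearly the same inpatient total. Only the SAP's restriction to patient-controlled analgesia clearly differs.
- *VAS is certainly inpatient only, or certainly extends to 3 months.* The record review may simply be a later reading of the same chart. The text does not settle it.

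**Conclusion.** The concern holds as an undefined efficacy decision with uncontrolled type I error, and it should be fixed. If any significant VAS recording counts, the two-sided false-positive chance is about 7 to 18%; if all must be significant, power at 40 per group is about 73 to 88% rather than 91%. Both ranges rest on the assumed two to five equally correlated recordings with complete data, so they show scale and do not predict this trial's error rate. The textual finding needs no such assumption: no primary outcome, deciding recording, summary or test is named. The opioid mismatch between SAP and Protocol is real but secondary.

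**What to change.** Before unblinding, amend the SAP and the matching Protocol text as follows.

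- **Primary.** Declare VAS primary, with one deciding test at two-sided .05: the treatment effect averaged over a fixed early inpatient window, for example the first two daily-round recordings. Estimate it from one mixed model for repeated measures using all available recordings, so that an early discharge or a refused score does not remove a patient who has at least one recording.
- **Limits.** Fix the window in advance. State that any follow-up VAS lies outside the primary analysis. Report per-recording differences as estimates with confidence intervals only.
- **Secondary.** Label opioid use, length of stay and discharge status (now named only in the Protocol) as secondary and supportive, with one named test each. Define opioid use once as the inpatient total, oral drugs included.
- **Exploratory.** Put subgroups and other chart outcomes here. Remove the open-ended allowance for further tests from the efficacy analysis.

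**Cost.** This is a wording change; the VAS scores are already recorded in routine care. An isolated significant time point can no longer be claimed. Averaging loses power if the effect fades: for the assumed 1.5 then 0.75 points it is about 72 to 82% at 40 per group and 98 to 99.5% at 100, with complete recordings. That argues for a short window. Missing scores would lower these figures somewhat, and the model relies on missingness being explained by the scores that were observed.
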